7.5. Radiation Related Adverse Events: Definition, Monitoring and Treatment

Acute radiation reactions occurring in the radiation volume field including esophagitis, pneumonitis, gastritis, soft tissue toxicity and other adverse events will be evaluated during the period of treatment and during subsequent visits. The adverse events will be graded according to National Cancer Institute (NCI) CTCAE v4.0.

Toxicity following SBRT treatment for liver and lung lesions appears to elicit minimal toxicity. With regard to liver SBRT, the actuarial rate of any Grade ≥ 3 toxicities have been reported to be 2% with only one instance of grade 3 soft tissue toxicity (13). Toxicity rates in patients receiving lung SBRT have been reported to 7.9% which included 1 instance of grade 3 dyspnea, chest wall fraction and skin reaction. Dosimetric considerations are important as centrally located lung lesions have been associated with significantly higher incidence of grade ≥ 3 toxicities (17%) compared with peripheral lesions (46%)(30).

7.6. Infusion Reactions and Fever Associated with Ipilimumab

7.6.1. Infusion Reactions

Since ipilimumab contains only human protein sequences, it is less likely that any allergic reaction will be seen in patients. However, it is possible that infusion of ipilimumab will induce a cytokine release syndrome that could be evidenced by fever, chills, rigors, rash, pruritus, hypo- or hypertension, bronchospasm or other symptoms. No prophylactic pre-medication will be given unless indicated by previous experience in an individual patient.

The following treatment guidelines are suggested:

Severe infusion reactions require the immediate interruption of ipilimumab and permanent discontinuation from further treatment.

Appropriate medical therapy including epinephrine, corticosteroids, intravenous antihistamines, bronchodilators, and oxygen should be available for use in the treatment of such reactions. Subjects should be carefully observed until the complete resolution of all signs and symptoms. In each case of an infusion reaction, the investigator should institute treatment measures according to the best available medical practice and institutional norms.

The following treatment guidelines are suggested:

CTCAE Grade 1 Allergic reaction/hypersensitivity (transient flushing or rash, drug fever < 38°C)

Treatment: Decrease the ipilimumab infusion rate by 50% and monitor closely for any worsening.

CTCAE Grade 1 or Grade 2 Allergic reaction/hypersensitivity manifesting only as delayed drug fever (starting after the completion of ipilimumab infusion)

Treatment: Maintain ipilimumab dose and infusion rate for future infusions. Consideration could be given to administration of acetaminophen or a nonsteroidal anti-inflammatory drug (NSAID) prior to the subsequent ipilimumab infusion, if not otherwise contraindicated in subjects. Dose and schedule of these agents is entirely at the investigator's discretion.

CTCAE Grade 2 Allergic reaction/hypersensitivity (Rash, flushing urticaria, dyspnea, drug fever ≥ 38°C)

Treatment: Interrupt ipilimumab infusion. Administer bronchodilators, oxygen, etc as medically indicated. Resume infusion at 50% of previous rate once infusion reaction has resolved or decreased to Grade 1 in severity, and monitor closely for any worsening.

CTCAE Grade 3 or Grade 4 Allergic Reaction/Hypersensitivity: A CTCAE Grade 3 hypersensitivity reaction (symptomatic bronchospasm, requiring parenteral medication(s), with or without urticaria; allergy-related edema/angioedema; hypotension) or a Grade 4 hypersensitivity reaction (anaphylaxis).

Treatment: Stop ipilimumab infusion immediately and disconnect infusion tubing from the subject. Administer epinephrine, bronchodilators, antihistamines, glucocorticoids, intravenous fluids, vasopressor agents, oxygen, etc, as medically indicated. Contact the PI and document as a serious adverse event. No further ipilimumab treatment to be administered.

Once an ipilimumab infusion rate has been decreased due to an infusion reaction, it should remain decreased for all subsequent infusions. If the subject has a second allergic/infusion reaction at the slower infusion rate, then the infusion should be stopped and the subject should be discontinued from ipilimumab.

If a subject experiences a Grade 3 or 4 allergic/infusion reaction at any time, the subject should be discontinued from ipilimumab.

7.7. Treatment of Ipilimumab Related Isolated Drug Fever

In the event of isolated drug fever, the Investigator must use clinical judgment to determine if the fever is related to the ipilimumab or to an infectious etiology.

If a patient experiences isolated drug fever, for the next dose, pre-treatment with acetaminophen or non-steroidal anti-inflammatory agent (Investigator discretion) should be instituted and a repeated antipyretic dose at 6 and 12 hours after ipilimumab infusion should be administered. The infusion rate will remain unchanged for future doses.

If a patient experiences recurrent isolated drug fever following pre-medication and post dosing with an appropriate antipyretic, the infusion rate for subsequent dosing should be decreased to 50% of

the previous rate. If fever recurs following infusion rate change, the Investigator should assess the patient's level of discomfort with the event and use clinical judgment to determine if the patient should receive further ipilimumab.

7.8. Concomitant, Prohibited and Restricted Therapies During the Study

7.8.1. Concomitant Therapies

- All patients should have antiemetic medications available once discharged from the clinic. Oral antiemetic medications should be prescribed and administered as needed, and adjusted during the cycle at the discretion of the treating investigator.
- If patients experience nausea and vomiting despite the premedication, the patient may take PRN antiemetics per treating physician's discretion.
- All patients may have emollient or lubricating creams to be placed on the corresponding SBRT field for symptomatic skin irritation after SBRT treatment completion at the discretion of the treating investigator.

Radiation outside of the SBRT treatment fields will also be allowed based on the treating physician discretion.

7.8.2. Prohibited Therapies

Patients in this study may not use vaccines for the treatment of cancer or prevention of disease for up to one month pre and post dosing with ipilimumab.

Concomitant systemic or local anti-cancer medications or treatments are prohibited in this study while receiving ipilimumab treatments, other than palliative (pain controlling) radiation therapy (RT) in situations that are not clearly indicative for PD.

Patients may not use any of the following therapies during the study:

- Any non-study anti-cancer agent (investigational or non-investigational);
- Any other investigational agents;
- Any other (non-CA184024 related) CTLA-4 / PD-1 / PDL-1 inhibitors or agonists;
- Immunosuppressive agents;
- Chronic systemic corticosteroids while receiving ipilimumab (as long as steroid replacement is significantly greater than what is required for physiologic replacement, i.e. in hypothyroidism);
- Any non-oncology vaccine therapies used for the prevention of infectious diseases (for up to 30 days prior to or after any dose of study drug).

8. Criteria for Evaluation

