8.1.1. Four weeks prior to study initiation

The following appropriate imaging studies for tumor assessment should be obtained within 4 weeks

prior to study initiation to provide diagnosis and measurement of target lesions.

- CT scans of the chest, abdomen and/or pelvis (contrast-enhanced preferred); or
- MRI of the abdomen or pelvis; or
- PET/CT scan (preferred)

The following imaging modalities are to be used in the event that above imaging modalities cannot be obtained

- Ultrasound (US) (special circumstances only, as described below in 9.4); or
- Chest radiograph (least preferred)

8.1.2. Within 3 weeks prior to radiation initiation.

- CT simulation for purposes of SBRT planning (as described in 6.2).

8.1.3. Within 2 weeks prior to study initiation.

The following studies should be obtained within 14 days prior to study initiation. All abnormal and normal results must be noted in the case report forms (CRF).

- Medical history to include determination of tumor-related symptoms.
- ECG
- Physical examination to include height, weight, vital signs, and performance status.
- CBC with differential and platelet count.
- Serum chemistry studies to include sodium, potassium, chloride, carbon dioxide, BUN, creatinine, glucose, magnesium, calcium, phosphorus, albumin, total protein, SGOT or SGPT, total bilirubin, alkaline phosphatase, and uric acid.
- Routine urinalysis.
- Serum evaluation for presence of Hepatitis B, C, and HIV. This will include (but not limited to) hepatitis C virus Ab, hepatitis B total Ig core Ab, hepatitis surface B Ag, and HIV 1/2 Antigen and Antibodies.
- Serum pregnancy test for females of childbearing potential within 7 days of registration.
- Mandatory tumor biopsy from any lesion at the discretion of PI and treating physician for tumor marker studies.
- Mandatory tumor biopsy from a lesion any time after SBRT for additional tumor marker studies.
- Tumor mutation biomarker analysis (whole exome sequencing) using left over tissue from a prior biopsy (optional procedure #1) and/or from the mandatory tumor biopsy samples.
- Initial serum samples for biomarker testing.

8.1.4. Monitoring following study completion.

Patients will return every 2-4 months for up to a year following completion of the last cycle of ipilimumab/BMS-986156/nivolumab with the following evaluations: CBC with differential and platelet count, serum chemistries, laboratory evaluation, and body imaging to assess for toxicity and disease response.

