10.2.4. Efficacy Analyses

Treatment success and clinical benefit will be defined as irCR or irPR or irSD, assessed using irRC (e.g. the best response obtained by a patient). Clinical benefit will be established as having irCR or irPR or irSD > 6 months. Measurements from all imaging, including those obtained during and after re-induction, will be considered in this analysis. Patients will be continuously evaluated for disease response via imaging until they are removed from the study. For secondary objectives a), b), and c), success probabilities will be estimated for each target separately (liver, lung) along with appropriate 95% confidence intervals. Safety comparisons among the groups will be assessed (primary end points) and efficacy comparisons between groups will be assessed with regard to the irRC outcomes while global, in-field irRC will be used for

hypothesis generating using Pearson chi-squared or Fisher exact tests. For secondary objective d) comparisons will be performed between group 2 and 3 as well as per treatment site (liver, or lung).

1. **Global irRC:** irRC that factors all lesions both index and non-index as outlined in 8.3.
2. **In-Field irRC:** irRC in which only SBRT-treated lesions will be considered and non-index lesions arising inside the SBRT PTV
3. **Out-Field irRC:** irRC in which only non SBRT-treated lesions will be considered and non-index lesions arising outside the SBRT PTV

For the secondary objective comparing the response between the arms. With 20 patients per arm, we would have 80% power using a two-sided 10% alpha with a chi-squared test to detect the following differences in response rates between treatment groups 44% vs 10%, 57% vs 20%, 68% vs 30% and 78% vs 40%. To increase statistical power, we may also combine the patients into a single dataset and fit a logistic regression model with response (CR+PR) as the outcome and SBRT dose, target (liver or lung) among other factors (including but not limited to: number of metastatic disease sites, number of prior treatments, primary cancer histology, age, pre-treatment KPS and Royal Marsden Score) as the predictors.

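### Best irRC response has no cut-off at the start of non-study anti-cancer therapy, so tumour shrinkage on a later drug can be scored as a response to the trial regimen

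*Combined protocol and SAP*

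**What the plan says.** **Which scans count.** Section 8.3 opens the best-response window after week 1 of cycle 5 (groups 1 and 2) or week 2 of cycle 3 (group 3) and gives no closing point. Section 10.2.4 adds: "Measurements from all imaging, including those obtained during and after re-induction, will be considered in this analysis". The only end it names is removal: "Patients will be continuously evaluated for disease response via imaging until they are removed from the study".

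**How long scans continue.** Section 8.1.4 brings patients back every 2 to 4 months for as long as a year after the last cycle, with "serum chemistries, laboratory evaluation, and body imaging to assess for toxicity and disease response". The group 3 calendar in section 12 marks irRC imaging in the follow-up column.

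**What is banned, and when.** Section 7.8.2 states "Patients may not use any of the following therapies during the study" and lists "Any non-study anti-cancer agent (investigational or non-investigational". It does not say when the study ends for this purpose. Another sentence in the same section limits a similar ban to the time on ipilimumab.

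**Who leaves the study.** Section 7.3.5 lists neither progression nor the start of other therapy as a reason for removal. It does list study completion, and any situation where the physician judges that continued treatment is not in the patient's interest. Section 7.3.4 lets patients who progress during combination treatment stay on trial at the physician's or PI's discretion.

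**The concern.** Many patients with advanced cancer move to another drug after progression. irPR is measured against the original baseline (8.5.1), so a patient who did not respond to the trial regimen can still meet irPR later, on the new drug. Nothing in 8.3 or 10.2.4 stops that scan from becoming the patient's best response.

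The estimates at stake are the success probabilities with 95% confidence intervals that 10.2.4 promises for secondary objectives a to c, and the exploratory comparison of groups. The share of patients who switch, and when they may do so, can differ between groups. The ipilimumab-limited ban does not reach group 3. In groups 1 and 2 it would lapse after the fourth dose (day 64), before nivolumab maintenance begins on day 85. Dose finding, DLTs and safety, which are the primary objectives, do not depend on this.

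**Working it through.** **1. The plan's own response figure.** Section 10.2.4 says "With 20 patients per arm, we would have 80% power using a two-sided 10% alpha with a chi-squared test" for the pairs "44% vs 10%, 57% vs 20%, 68% vs 30% and 78% vs 40" (per cent). The inputs are n = 20 per arm and two-sided alpha 0.10 (z = 1.645). The formula, with pooled variance under the null and no continuity correction, is

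power = Φ{ (|p1 − p2| − 1.645 √[2 p̄(1 − p̄)/n]) / √[(p1(1 − p1) + p2(1 − p2))/n] }.

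For 44% v 10%: p̄ = 0.27, so (0.34 − 1.645 × 0.1404)/0.1297 = 0.84, and power is 0.800. The other three pairs give 0.794, 0.794 and 0.807. The stated 80% is reproduced and does not depend on this concern.

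**2. Does the text stop the count at other therapy?**

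| Place | What it fixes | What it leaves open |
|---|---|---|
| 8.3 | start of the best-response window | its end |
| 10.2.4 | all imaging until removal | whether a switch ends it |
| 8.1.4, group 3 calendar | response imaging in the follow-up year | whether those scans count |
| 7.3.5 | reasons for removal | progression and new therapy not named |
| 7.8.2 | non-study agents banned | the period of the ban |

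No section ends response assessment at non-study therapy.

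**3. How long is the window?** On full treatment the last nivolumab dose falls on day 85 + 25 × 28 = 785 (groups 1 and 2) or day 113 + 21 × 28 = 701 (group 3), with up to a year of imaging after that. For a patient who stops early, the follow-up year starts early too.

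**4. Illustrative size.** From the documents: 60 patients (10.2.5), and 10% out-of-field irPR and 23% clinical benefit in the earlier ipilimumab plus SBRT trial (3.3). Assumed, not in the documents: a share q = 30% to 70% of patients without benefit start another drug and are still scanned, and a share r = 5% to 20% of those reach irPR against baseline.

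- Without benefit: 60 × 0.77 = 46.2.
- Responders on the trial regimen: 60 × 0.10 = 6.
- Extra responders: 46.2 × q × r, from 46.2 × 0.30 × 0.05 = 0.7 to 46.2 × 0.70 × 0.20 = 6.5.
- Reported rate: (6 + 0.7)/60 = 11.2% to (6 + 6.5)/60 = 20.8%.

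A wider grid treats all non-responders as able to switch: reported rate = p + (1 − p) × f × q′, where f is the share who switch and are still scanned and q′ their chance of irPR or irCR. With p = 10%, f = 25% to 75% and q′ = 5% to 30%, this gives 11.1% to 30.2%. The middle case (f = 50%, q′ = 20%) gives 0.10 + 0.90 × 0.50 × 0.20 = 19.0%. With f = 0 it stays at 10%.

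**5. If only one group is affected.** With both true rates at 10% and 20 per group, the exact rejection rate of the 10%-level chi-squared test is 10.3% without contamination. It is 13.8% if one group reads 14.5% (f = 50%, q′ = 10%) and 21.4% if it reads 19.0%.

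**The case against.** **The follow-up year may already lie outside the window.** Section 7.3.5 lists study completion as a reason for withdrawal, 8.1.4 is headed as monitoring after completion, and 10.2.4 evaluates response only until removal. Section 8.2.3, which also describes follow-up, lists no imaging. The best-interest clause in 7.3.5 could also remove a patient at about the time of a switch. This reading is possible, but it sits badly with 8.3, which sets no end, and with 8.1.4 and the group 3 calendar, which schedule these scans for response. The best-interest clause is a judgement about treatment and does not date-limit the scans. An analyst cannot tell from the text which scans count.

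**Other agents are barred during treatment.** Sections 1, 7 and 7.8.2 all say so. That narrows the problem to the time after trial drugs stop, but none of them says whether the follow-up year is covered.

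**The figures are assumptions.** This stands. The 10% and 23% come from ipilimumab plus SBRT, whereas group 1 has no SBRT (hence no in-field and out-of-field split) and group 3 no ipilimumab. A false irPR also needs a confirmed fall of at least 50% from baseline with new measurable lesions added to the burden, which favours the lower end of the range.

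**A stronger reading about survival.** A reader might infer that the ban forces progressing patients out of the study, so that overall survival is censored at progression and either response or survival must be biased. The documents do not support this. No section says that breaching 7.8.2 or progressing ends follow-up, and 7.3.4 allows patients to stay on trial despite progression. The survival paragraph of 10.2.4 is silent on vital status after removal, and silence is not a censoring rule.

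**Conclusion.** The gap is real but limited. The plan's rule counts all imaging, imaging for response runs into the follow-up year, and nothing stops the count at non-study therapy. Following the text can therefore credit a later drug's effect to the trial regimen. Under the narrower assumptions above, a true 10% would read about 11% to 21%. The documents supply neither the switching rate nor the response rate on later therapy, so this range illustrates scale and is not an estimate of bias. The effect vanishes if no patient is scanned after a switch.

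It bears on the estimates for secondary objectives a to c and on comparisons that 10.2.1 calls exploratory, not on the primary safety objectives or the stated power. No claim of survival bias is made. The change should be made before analysis, because the date of a switch may not be recoverable later if it is not collected.

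**What to change.** - In 8.3 and 10.2.4, state that only scans before the first non-study systemic anti-cancer therapy count toward global, in-field and out-field best irRC response. Any confirming scan would then also have to precede it. Scans during and after re-induction with trial drugs continue to count, as now.
- Record the date and type of the first non-study therapy on the case report form.
- Reconcile the period of the ban in 7.8.2 with the removal list in 7.3.5 and the follow-up year in 8.1.4, for all three groups. No view is taken here on which therapies should be allowed or when.
- As a clarification, add that vital status is followed regardless of later therapy.

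The cost is a few sentences and a small CRF addition. The reported response rate may be slightly lower.

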8.1. Evaluations at Baseline

Notice: On-study tests/visits that must occur within a defined time frame shall have a standing window of allowance that is equal to +/- 3 days for any laboratory testing unless patient/logistical/medical reasons intervene. Overlapping baseline tests can be combined with tests required for cycle 1 of drug administration as long as these baseline tests occur within 3 days before cycle 1.

8.1.1. Four weeks prior to study initiation

The following appropriate imaging studies for tumor assessment should be obtained within 4 weeks

prior to study initiation to provide diagnosis and measurement of target lesions.

- CT scans of the chest, abdomen and/or pelvis (contrast-enhanced preferred); or
- MRI of the abdomen or pelvis; or
- PET/CT scan (preferred)

The following imaging modalities are to be used in the event that above imaging modalities cannot be obtained

- Ultrasound (US) (special circumstances only, as described below in 9.4); or
- Chest radiograph (least preferred)

8.1.2. Within 3 weeks prior to radiation initiation.

- CT simulation for purposes of SBRT planning (as described in 6.2).

8.1.3. Within 2 weeks prior to study initiation.

The following studies should be obtained within 14 days prior to study initiation. All abnormal and normal results must be noted in the case report forms (CRF).

- Medical history to include determination of tumor-related symptoms.
- ECG
- Physical examination to include height, weight, vital signs, and performance status.
- CBC with differential and platelet count.
- Serum chemistry studies to include sodium, potassium, chloride, carbon dioxide, BUN, creatinine, glucose, magnesium, calcium, phosphorus, albumin, total protein, SGOT or SGPT, total bilirubin, alkaline phosphatase, and uric acid.
- Routine urinalysis.
- Serum evaluation for presence of Hepatitis B, C, and HIV. This will include (but not limited to) hepatitis C virus Ab, hepatitis B total Ig core Ab, hepatitis surface B Ag, and HIV 1/2 Antigen and Antibodies.
- Serum pregnancy test for females of childbearing potential within 7 days of registration.
- Mandatory tumor biopsy from any lesion at the discretion of PI and treating physician for tumor marker studies.
- Mandatory tumor biopsy from a lesion any time after SBRT for additional tumor marker studies.
- Tumor mutation biomarker analysis (whole exome sequencing) using left over tissue from a prior biopsy (optional procedure #1) and/or from the mandatory tumor biopsy samples.
- Initial serum samples for biomarker testing.

8.1.4. Monitoring following study completion.

Patients will return every 2-4 months for up to a year following completion of the last cycle of ipilimumab/BMS-986156/nivolumab with the following evaluations: CBC with differential and platelet count, serum chemistries, laboratory evaluation, and body imaging to assess for toxicity and disease response.

At the end of the study period, Bristol-Myers Squibb Company will not continue to supply study drug to subjects/investigators unless the Sponsor-Investigator chooses to extend their study. The investigator is responsible to ensure that the subject receives appropriate standard of care or other appropriate treatment in the independent medical judgement of the investigator to treat the condition under study.

